6.1.3. Adapted ATP Cohort

When presenting different time points, the adapted ATP cohort will be used to denote that for each time point, the corresponding ATP cohort for immunogenicity has been used.

More specifically:

• the analyses on the pre and post primary time points will be based on the ATP cohort for immunogenicity defined in MenACWY-TT-027.

MenACWY-TT-100 (C0921004)

- the analyses on Months 12, 24, 36, 48, and 60 time points will be based on the ATP cohort for persistence in MenACWY-TT-028, -029, -030, -031, and -032 respectively.
- the analyses on Months 78, 90, 102, 114, and 126 time points are based on the ATP cohort for persistence at Months 78, 90, 102, 114, and 126 in MenACWY-TT-100, respectively.

6.1.4. Total Enrolled Cohort

The total enrolled cohort will include all the subjects enrolled in the study irrespective of the visit at which they are enrolled. Lack of enrollment in MenACWY-TT-100 is not exclusionary.

The total enrolled – persistence cohort will include all subjects with any immunogenicity result available at any time point, which means data from Studies MenACWY-TT-027/-028/-029/-030/-031/-032 and all time points from Study -100. More specifically, this cohort will include subjects with immunogenicity results available at any time point who also belong to the corresponding total vaccinated cohort (Study MenACWY-TT-027) or total cohort (Studies MenACWY-TT-028, -029, -030, -031, -032, and -100) regardless of their enrollment in Study MenACWY-TT-100.

6.2. Booster Cohort

The requirements for the persistence cohorts are summarized in Table 3. Details are included in Section 6.2.1 through Section 6.2.4.

 Table 3.
 Summary Description of Cohorts Associated with Booster Analyses

Booster Total Vaccinated Cohort	Booster Total Vaccinated for Immunogenicity Cohort	Booster ATP for Safety Cohort	Booster ATP Immunogenicity MenC Cohort	Booster ATP Immunogenicity MenAWY Cohort
Vaccinated in MenACWY-TT-027	Vaccinated in MenACWY-TT-027	Vaccinated in MenACWY-TT-027 with assigned vaccination	Vaccinated in MenACWY-TT-027 with assigned vaccination	Vaccinated in MenACWY-TT-027 with assigned vaccination
Received booster dose	Received booster dose	Received booster dose Met all inclusion/exclusion for MenACWY-TT-100	Met all inclusion/exclusion for MenACWY-TT-100	Met all inclusion/exclusion for MenACWY-TT-100
	At least 1 postbooster titer available	Have not received a vaccine not specified or forbidden in protocol	Have not received a vaccine not specified or forbidden in protocol	Have not received a vaccine not specified or forbidden in protocol
		Admin site of booster vaccination known	Admin site of booster vaccination known	Admin site of booster vaccination known

MenACWY-TT-100 (C0921004)

Table 3. Summary Description of Cohorts Associated with Booster Analyses

Booster Total Vaccinated Cohort	Booster Total Vaccinated for Immunogenicity Cohort	Booster ATP for Safety Cohort	Booster ATP Immunogenicity MenC Cohort	Booster ATP Immunogenicity MenAWY Cohort
		Not excluded from ATP cohort for Year 10, unless reason was (1) missing window or (2) no immuno results at Year 10	Not excluded from ATP cohort for Year 10, unless reason was (1) missing window or (2) no immuno results at Year 10 Comply with protocol procedures No elimination criteria during the study. Member of booster ATP for safety cohort	Not excluded from ATP cohort for Year 10, unless reason was (1) missing window or (2) no immuno results at Year 10 Comply with protocol procedures No elimination criteria during the study. Member of booster ATP for safety cohort
			MenC titer available post booster No unforeseen vaccinations from 30 days before booster until the postvaccination bleed No MenC or MenACWY conjugate vaccine between MenACWY-TT-027 vaccination and booster due to suboptimal MenC response	MenA, W-135, or Y titer available No unforeseen vaccinations from 30 days before booster until the postvaccination bleed No MenACWY conjugate vaccine between MenACWY-TT-027 vaccination and booster due to suboptimal response
			Interval for inclusion is 21-48 days from vaccination to post bleed	Receiving monovalent MenC conjugate due to suboptimal response is not exclusionary Interval for inclusion is 21-48 days from vaccination to post bleed
			Medications/products/v accines and/or no intercurrent medical conditions that may lead to the exclusion of a subject according to Protocol sections 6.5.2 and 6.6	Medications/products/v accines and/or no intercurrent medical conditions that may lead to the exclusion of a subject according to Protocol sections 6.5.2 and 6.6

Persistence cohorts are described in more detail in Section 6.2.1, Section 6.2.2, Section 6.2.3, and Section 6.2.4.

MenACWY-TT-100 (C0921004)

6.2.1. Booster Total Vaccinated Cohort

The booster total vaccinated (BTV) cohort for safety will include all vaccinated subjects in the primary vaccination Study MenACWY-TT-027 (108658) with a documented booster vaccine administration.

For the analysis of immunogenicity after the booster vaccination the BTV cohort will include all subjects for whom data concerning post–booster immunogenicity endpoint measures are available.

6.2.2. Booster ATP Cohort for Safety

The booster ATP cohort for safety will include all subjects:

- who met all inclusion criteria and no exclusion criteria for the study.
- who received a dose of study vaccine MenACWY-TT, Meningitec, or Mencevax ACWY in the primary study (MenACWY-TT-027) according to their vaccine group.
- who did not receive a vaccine not specified or forbidden in the protocol (subjects who
 received a vaccine not foreseen by the study protocol from 30 days before until
 30 days after the study vaccine dose will be eliminated from the ATP cohort for
 safety if the vaccine not foreseen by the protocol was administered before the
 postvaccination blood sample).
- who received a booster dose of study vaccine MenACWY-TT in the booster epoch.
- for whom the administration site of the vaccine is known.
- who were not excluded from either ATP cohort for persistence at Month 126 (ie, MenC or MenAWY), unless the reason for exclusion was either non-compliance with the protocol-defined serum sampling windows or a lack of availability of immunogenicity results at Month 126 (Year 10, prebooster vaccination).

6.2.3. Booster ATP Cohort for Immunogenicity - MenC

The booster ATP cohort for immunogenicity – MenC will include all subjects who:

- are evaluable (ie, those meeting all eligibility criteria, complying with the procedures defined in the protocol and with no exclusion criteria during the study).
- are from the booster ATP cohort for safety.
- have assay results available for antibodies against MenC antigen for the blood sample taken 1 month post-vaccination, and

MenACWY-TT-100 (C0921004)

- were not administered a vaccine not foreseen by the study protocol from 30 days before the booster administration until the post-vaccination blood sample, and
- have not received a monovalent MenC conjugate vaccine or MenACWY conjugate vaccine because of suboptimal response to *N meningitidis* group C between the vaccination in the primary study (MenACWY-TT-027 [108568]) and the booster vaccine in this study, and
- have an interval between Visit 5 and Visit 6 of 21 to 48 days, inclusive.

6.2.4. Booster ATP Cohort for Immunogenicity –MenAWY

The booster ATP cohort for immunogenicity – MenAWY cohort will include all subjects who:

- are evaluable (ie, those meeting all eligibility criteria, complying with the procedures defined in the protocol and with no exclusion criteria during the study).
- are from the booster ATP cohort for safety.
- have assay results available for antibodies against at least 1 of the 3 antigens (MenA or MenW-135 or MenY) for the blood sample taken 1 month after vaccination, and
- were not administered a vaccine not foreseen by the study protocol from 30 days before the booster administration until the post-vaccination blood sample and
- have not received a MenACWY conjugate vaccine because of sub-optimal response between the vaccination in the primary study (MenACWY-TT-027 [108568]) and the booster vaccine in this study (if a subject previously received monovalent MenC conjugate vaccine because of suboptimal response to *N meningitidis* group C after vaccination in the primary study MenACWY-TT-027 (108568), the subject can still be included in the booster ATP cohort for immunogenicity – MenAWY), and
- have an interval between Visit 5 and Visit 6 of 21 to 48 days, inclusive.

7. STATISTICAL METHODS

7.1. Persistence Analyses

7.1.1. Analysis of Demographics/Baseline Characteristics

Demographic characteristics of subjects in each study cohort will be tabulated: age (in years) at Month X (with the range and standard deviation), sex, and geographic ancestry.

MenACWY-TT-100 (C0921004)

The distribution of subjects enrolled in this study among the study sites will be tabulated as a whole and per group. The reasons for not enrolling will be summarized for all subjects who were vaccinated in the primary study (MenACWY-TT-027 [108658]).

7.1.2. Analysis of Persistence

The persistence analyses will be based on the adapted ATP cohort. If for any vaccine group, at any time point, the percentage of subjects who have serological results but are otherwise excluded for the corresponding ATP cohort is higher than 10%, a second analysis based on the total enrolled cohort will be performed to complement the ATP analysis. The percentage of subjects with excluded serological results will compiled separately for the MenC ATP persistence cohort and the MenAWY ATP persistence cohort.

Different laboratories performed the rSBAs and hSBAs at different time points. rSBAs were performed either by GSK or Public Health England (PHE) (see Table 4). hSBAs were performed either by GSK or Neomed (Neomed was a GSK facility until it was spun off as an independent company) (see Table 5). Furthermore, GSK did not perform hSBAs for 2-<6 year subjects. The consequences will be described in Section 7.1.2.1, Section 7.1.2.2, and Section 7.1.3.

Table 4. Description of Laboratories Performing rSBAs by Time Point

		GSK		PHE	
Study MenACWY-	Time Point	1-<2 years	2-<11 years	1-<2 years	2-<11 years
TT-027	Baseline (Month 0)	✓	√		
	Month 1	✓	√		
TT-028	Year 1	✓	✓		
TT-029	Year 2	✓	✓		
TT-030	Year 3	✓	✓		
TT-031	Year 4	✓	✓	√	✓
TT-032	Year 5			✓	✓
TT-100	Month 78 (Year 6)			√	✓
	Month 90 (Year 7)			√	✓
	Month 102 (Year 8)			✓	✓
	Month 114 (Year 9)			✓	✓
	Month 126 (Year 10)			√	✓
	Month 127			√	√

Abbreviations: rSBA = serum bactericidal assay against *Neisseria meningitidis* using rabbit complement.

MenACWY-TT-100 (C0921004)

Table 5. Description of Laboratories Performing hSBAs by Time Point

		GS	GSK		Neomed	
Study MenACWY-	Time Point	1-<2 years	6-<11 years	1-<2 years	2-<11 years	
TT-027	Baseline (Month 0)	✓	✓			
	Month 1	✓	✓			
TT-028	Year 1	✓	√			
TT-029	Year 2	✓				
TT-030	Year 3	✓				
TT-031	Year 4	✓				
TT-032	Year 5	✓				
TT-100	Month 78 (Year 6)			√	√	
	Month 90 (Year 7)			√	√	
	Month 102 (Year 8)			✓	√	
	Month 114 (Year 9)			√	√	
	Month 126 (Year 10)			√	√	
	Month 127			✓	√	

Abbreviations: hSBA = serum bactericidal assay against Neisseria meningitidis using human complement.

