- Administration of a meningococcal vaccine of any serogroup not foreseen by the study protocol at any time during the study period.
- Immunoglobulins and/or any blood products administered during the study period.
- Drug and/or alcohol abuse.

A detailed, comprehensive list of reasons for elimination from ATP analyses will be established at the time of data cleaning.

6.6. Intercurrent medical conditions that may lead to elimination of a subject from ATP analyses

At each study visit subsequent to the vaccination visit, it must be verified if the subject has experienced or is experiencing any intercurrent medical condition. If it is the case, the condition(s) must be recorded in the eCRF.

The following may result in the elimination of subjects from the ATP cohort for immunogenicity, but not necessarily from the study:

- Occurrence of meningococcal disease*.
- Any confirmed or suspected condition that has the capability of altering the subject's immune response (e.g. intercurrent lymphopenia).
- Any confirmed or suspected immunosuppressive or immunodeficient condition, including Human immunodeficiency virus (HIV) infection based on medical history and physical examination (no laboratory testing required).

- Diagnosis of any serious chronic illness.
- * Occurrence of meningococcal disease should be recorded as an SAE.

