10.4.1. Persistence cohorts

10.4.1.1. Total cohort at Month X

The Total cohort at Month X will include all vaccinated subjects in the vaccination stage of study MenACWY-TT-027 (108658) who return for the Month X follow-up. For the analysis of persistence, this will include all vaccinated subjects for whom data concerning persistence endpoint measures are available.

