10.5.1.2. Analysis of persistence

For each Month X: The analysis of antibody persistence for MenC will be based on the ATP cohort for persistence – MenC – adapted for each time point. The analysis of antibody persistence for MenA, MenW-135 and MenY will be based on the ATP cohort for persistence – MenAWY – adapted for each time point. If, for any vaccine group, the percentage of subjects who come back for the Month X follow-up with serological results excluded from the ATP cohort is higher than 10%, a second analysis based on the Total Vaccinated Cohort Month X will be performed to complement the ATP analysis.

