4. OBJECTIVES

4.1. Primary Objectives

Long-term persistence phase: 6, 7, 8, 9, and 10 years after primary vaccination with MenACWY-TT, Meningitec, or Mencevax ACWY in Study MenACWY-TT-027:

- To evaluate the long-term persistence of the serum bactericidal (antibody) titers induced by MenACWY-TT vaccine as compared to Meningitec when administered to individuals 1-<2 years of age in terms of the percentage of subjects with *Neisseria meningitidis* group A (MenA), group C (MenC), group W-135 (MenW-135), and group Y (MenY) titers ≥1:8, ≥1:128 and geometric mean titers (GMTs) as measured by a serum bactericidal assay using rabbit complement (rSBA) in those subjects who received MenACWY-TT, and group C (MenC) rSBA titers ≥1:8, ≥1:128 and GMTs in those subjects who received Meningitec.
- To evaluate the long-term persistence of the serum bactericidal (antibody) titers induced by MenACWY-TT vaccine as compared to Mencevax ACWY when administered to individuals 2-10 years of age in terms of the percentage of subjects with *Neisseria meningitidis* group A (MenA), group C (MenC), group W-135 (MenW-135), and group Y (MenY) titers ≥1:8, ≥1:128 and GMTs as measured by rSBA.

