8. STATISTICAL CALCULATIONS

8.1. Derived and Transformed Data

- Age in years will be calculated as (date minus date of birth)/365.25, rounded down to nearest integer.
- Duration from primary vaccination to any persistence time point will use day of primary vaccination as Day 0. Duration from booster will use day of booster vaccination as Day 0.
- Activity date is defined as the date associated with any activity performed at indicated visit.
- For a given subject and a given immunogenicity measurement, missing or non-evaluable measurements will not be replaced. Therefore, an analysis will exclude subjects with missing or non-evaluable measurements.
- The cutoff values for the assays are defined by the laboratory before the analysis and are described in Section 5.7.3 of the protocol.

MenACWY-TT-100 (C0921004)

- A seronegative subject is a subject whose titer is below the cutoff value.
- A seropositive subject is a subject whose titer is greater than or equal to the cutoff value.
- GMTs are calculated by taking the antilog of the mean of the log titer transformations. Antibody titers below the cutoff value of the assay will be given an arbitrary value of half the cutoff value for the purpose of the GMT calculation.
- rSBA vaccine response for groups A, C, W-135, and Y after the booster dose is defined as:
 - For initially seronegative subjects (pre-vaccination titer <1:8): rSBA antibody titers ≥1:32 1 month after vaccination, and
 - For initially seropositive subjects (pre-vaccination titer ≥1:8): a 4-fold increase in rSBA antibody titers 1 month after vaccination.
- hSBA vaccine response for groups A, C, W-135, and Y after the booster dose is defined as:
 - For initially seronegative subjects (pre-vaccination hSBA titer <1:4): hSBA antibody titers ≥1:8 1 month after vaccination, and
 - For initially seropositive subjects (pre-vaccination hSBA titer ≥1:4): a 4-fold increase in hSBA antibody titers 1 month after vaccination.
- For subjects who received MenC vaccine because they were suboptimal responders during the persistence phase of the MenACWY-TT-027 study, all subsequent persistence results for MenC will be replaced by half the cutoff in order to reflect the immunogenicity of the subjects, had they not been revaccinated. This includes Month 126. However, there will be no adjustment to postbooster MenC titers.

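### If the complementary persistence analysis is run, titres drawn after an unplanned meningococcal vaccine given post-entry enter it unadjusted and can be read as persistence of the primary dose

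*SAP*

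**What the plan says.** The primary objective (SAP 4.1) begins: "To evaluate the long-term persistence of the serum bactericidal (antibody) titers induced by MenACWY-TT vaccine". The main persistence analysis uses the ATP cohort for each time point. SAP 6.1.2 keeps out of that cohort anyone given a meningococcal vaccine not planned in study 027, apart from MenC vaccine given to suboptimal responders.

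SAP 7.1.2 adds a conditional check. Its trigger, which a single group at a single visit is enough to meet, is that "the percentage of subjects who have serological results but are otherwise excluded for the corresponding ATP cohort is higher than 10"%. Once it is met, "a second analysis based on the total enrolled cohort will be performed to complement the ATP analysis". SAP 6.1.4 defines that set: "The total enrolled cohort will include all the subjects enrolled in the study irrespective of the visit at which they are enrolled". Protocol 10.5.1.2 names a different set: "a second analysis based on the Total Vaccinated Cohort Month X will be performed to complement the ATP analysis". For persistence, the total cohort in Protocol 10.4.1.1 is equally open: "this will include all vaccinated subjects for whom data concerning persistence endpoint measures are available".

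Protocol 6.5.2 lists among the events that may cost a subject ATP evaluability, without requiring withdrawal: "Administration of a meningococcal vaccine of any serogroup not foreseen by the study protocol at any time during the study period".

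The plan has one rule for titres after revaccination. Under SAP 8.1, later MenC persistence results of suboptimal responders given MenC vaccine during the persistence phase of study 027 are set to half the cutoff, "in order to reflect the immunogenicity of the subjects, had they not been revaccinated". Protocol 4.3 identifies that phase as studies 028 to 032.

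**The concern.** The complementary analysis exists to show whether leaving subjects out of the ATP cohort distorted the result. Most reasons for exclusion, such as a missed visit window, leave the titre a valid measure of what the primary dose left behind. A meningococcal vaccine from outside the study does not: for the serogroups it contains, the later titre reflects the new dose. If both kinds of excluded result are pooled, a gap between the two analyses cannot be interpreted. A higher total-cohort result might be taken to mean that the ATP analysis understates persistence, when it only reflects other vaccines.

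The plan foresees the event. The booster ATP cohorts exclude subjects who received a MenACWY conjugate vaccine for suboptimal response between the primary and booster doses (SAP 6.2.3 and 6.2.4). Investigators also receive titres and group allocation at each persistence time point (Protocol 5.7.5), so outside vaccination could be related to low titres. Because ATP exclusions for this reason carry forward, affected subjects accumulate towards Year 10.

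**Working it through.** **1. Tracing one subject through the text.** Take a subject who enters at Month 78 and receives an outside quadrivalent vaccine before Month 102.

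| Question | Answer | Source |
|---|---|---|
| Could the vaccine have preceded entry? | No. Prior outside meningococcal vaccination bars entry, except MenC vaccine for suboptimal response | Protocol 4.3 |
| Are entry criteria rechecked later? | No, only at the subject's first visit | Protocol Table 4, footnote 2 |
| Is the subject withdrawn? | No | Protocol 6.5.2 |
| In the ATP cohort at Month 102? | No | SAP 6.1.2 |
| In the total enrolled cohort? | Yes | SAP 6.1.4 |
| Are the titres adjusted? | No. The half-cutoff rule covers MenC vaccine given in studies 028 to 032 | SAP 8.1, Protocol 4.3 |

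A Month 78 sample is always a first-visit sample in this study. Exposure is therefore limited in practice to Years 7 to 10.

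**2. The plan's own figures.** The documents give no bias figure and no outside-vaccination rate. The planned Year 10 group sizes are 122 and 41 (Protocol 10.3); 10% annual dropout gives 183 × 0.9⁴ = 120.1 and 61 × 0.9⁴ = 40.0, close to those stated. Table 17 also reproduces: 98/122 has an exact 95% interval of 72.2 to 87.0. At these sizes the trigger needs 13 of 122 (10.7%; 12 is 9.8%) or 5 of 41 (12.2%; 4 is 9.8%) excluded subjects, for any reason.

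**3. Within-group shift.** Let p be the percentage at or above 1:8 without outside vaccination, q the share vaccinated, and r the percentage of those at or above 1:8. If vaccination is unrelated to titre:

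observed = (1 − q)p + qr, so shift = q(r − p).

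The values of p are the Year 5 percentages in Protocol 1.2. The protocol describes these only as detectable antibody, so reading them as titres ≥1:8 is an assumption. So are r = 98% and every q.

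| Group, serogroup | p | q = 0 | q = 5% | q = 10% |
|---|---|---|---|---|
| ACWY<2, MenW-135 | 34.7 | 34.7 | 37.9 | 41.0 |
| ACWY<2, MenY | 42.9 | 42.9 | 45.7 | 48.4 |
| ACWY≥2, MenW-135 or MenY | 78.6 | 78.6 | 79.6 | 80.5 |

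For example, 0.90 × 34.7 + 0.10 × 98 = 31.2 + 9.8 = 41.0. Reaching q = 10% over four years needs 1 − 0.9^(1/4) = 2.6% vaccinated per year.

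**4. Difference between ACWY≥2 and MenPS.** This is the only between-group comparison planned for MenA, MenW-135 and MenY (SAP 7.1.2.2). Assume 40% in MenPS for MenW-135 or MenY, so the true difference is 78.6 − 40 = 38.6 points.

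- 10% vaccinated in both groups: 0.90 × 38.6 = 34.7 (shrinks).
- 10% in MenPS only: 78.6 − (40 + 0.10 × 58) = 78.6 − 45.8 = 32.8 (shrinks).
- 10% in ACWY≥2 only: (78.6 + 0.10 × 19.4) − 40 = 40.5 (widens).

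The difference widens once the ratio of q in ACWY≥2 to q in MenPS exceeds (98 − MenPS%)/(98 − 78.6). That ratio is 78/19.4 = 4.0, 58/19.4 = 3.0 or 38/19.4 = 2.0 for MenPS at 20%, 40% or 60%.

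**5. If low-titre subjects are the ones vaccinated.** Suppose 10% of ACWY<2 are vaccinated, all of them below 1:8 for MenW-135 and all responding (r = 100%). As observed, the total cohort reads 34.7 + 10 = 44.7%. After removing their later titres it reads 34.7/0.90 = 38.6%. Removal cuts the error from 10.0 to 3.9 points but does not eliminate it.

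**The case against.** The strongest reply is that a total cohort is meant to be as-observed, as a deliberate contrast to ATP. The ATP analysis already addresses the objective and excludes outside vaccinees, the second analysis is conditional, and Protocol 10.6 makes all analyses descriptive. Vaccination history is recorded at every persistence visit, so any discrepancy could be explained afterwards. This stands as a limit on importance. It does not close the gap: SAP 8.1 states the half-cutoff rule without limiting it to a cohort, so the complementary analysis is already not as-observed for those MenC results.

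A reader might infer more than the documents support:

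- **That triggering the rule implies bias.** The 10% counts every ATP exclusion, including missed windows, medication, medical conditions and carried-forward exclusions. If nobody had a relevant vaccine after entry, the bias is zero.
- **That group differences always shrink.** They shrink at equal or MenPS-heavier vaccination when ACWY≥2 is truly higher, but can widen otherwise (step 4).
- **That Year 6 is exposed.** The entry criterion makes this unlikely.

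It can also be said that removal departs from the SAP's own reasoning. SAP 10 retains MenC revaccinees because dropping them would overestimate persistence. That is fair. Since ATP drops the same outside vaccinees, agreement between the two analyses would not reveal selection of this kind. For that reason the as-observed result should be kept alongside.

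**Conclusion.** The gap is real but conditional. It needs the trigger to be met and some subjects to have received, after entry, an unplanned meningococcal vaccine containing the serogroup analysed. Within-group persistence in the complementary analysis can then be biased upward, in practice at Years 7 to 10, and the ACWY≥2 versus MenPS difference can move either way. The same gap applies to MenC titres outside the half-cutoff rule.

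The size is unknown. The 6.3-point rise for ACWY<2 MenW-135 (34.7% to 41.0%) rests on an assumed 10% vaccinated, an assumed 98% response, Year 5 values standing in for later years, and vaccination unrelated to titre. ACWY≥2 MenW-135 and MenY would move by about 2 points under the same assumptions.

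A reader might conclude that the trial's main persistence result is compromised. It is not: the primary ATP analysis is unaffected. The point is worth fixing because the check could mislead in the situation it is meant to clarify.

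**What to change.** Add to SAP 7.1.2 and 8.1: when the complementary total-cohort persistence analysis is run, titres for any serogroup contained in a meningococcal vaccine not planned in MenACWY-TT-027 or MenACWY-TT-100 are excluded from the date of that vaccine. MenC results under the half-cutoff rule stay as they are, and all other ATP-excluded results are retained.

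Show the as-observed version beside it as a labelled sensitivity analysis. Report the number of subjects and samples set aside, by group and time point.

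Use one cohort name and definition in Protocol 10.5.1.2 and SAP 7.1.2, which now name different sets.

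The cost is a short SAP addition, one data step and one extra set of tables; the vaccination history needed is already collected (Protocol Table 4). Some upward bias remains if low-titre subjects are the ones vaccinated, and the report should say so.
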